#### 5.3.2 For case II

The same *Anopheline* species and same procedure implemented in all cases regarding cone bioassay, following the regeneration of the insecticide or bioavailability given by the manufacturer. The bioassay will be carried on randomly selected 30 sample nets from each type every six months. At the end of three years, at least 80% of nets meet the cut off criteria for either the WHO cone bioassay test or the tunnel test, and then the product meets the definition for a LLINs.

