## 3.2 Specific objectives:

The specific objectives of this protocol is to:

- ✓ Determine the bio-efficacy of LLINs against *Anopheles arabiensis*, principal malaria vector insecticidal activity
- ✓ Evaluate wash resistance of LLINs through repeated community wash in the field setting
- ✓ Test the survivorship and fabric integrity of LLINs in various environments and cultural settings
- ✓ Evaluate the insecticide content at the beginning and over time as they are routinely used by people in various settings
- ✓ Determine the acceptability of LLINs by the community

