# 4.1 Study site

The study can be conducted in all representative malarious areas of Ethiopia. The study site will be selected based on conditions of the location that may affect bed net usage, accessibility and local support and on-ground capacity. The sites should represent the environments and cultural settings in which LLINs can be distributed. The study site should be large enough to allow selection of sufficient numbers of nets during follow-up.

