## 4.3 Sampling

If sampling is done at a net level, a list of randomly selected nets with their unique code numbers and information on the household to which they distributed (e.g. Household identification, name of head of household, Global Positioning System (GPS)should be given to the staff who are sampling the nets in the field, who should sample all the nets on the list. If sampling is one at the household level, the number of nets distributed to each household should be estimated, and then the number of households required to reach the estimated sample size should be determined. Sampling should be simple random sampling, so that there is an equal probability of selection of each household in the list. Determination of the sample size should take into account the precision and the difference necessary to detect each outcome measure for the different LLINs products.

The estimated sample size should also take into account variations between nets and between households. It should be based on the outcome that requires the largest sample, although subsamples can be taken for some measures (e.g. bioefficacy). The sample net should be labelled by the study organizers or the manufacturer, allowing easy reading of stored information (product, batch, manufacturing data, distribution date), as long as it has not faded or the label has been lost. Sample size on the basis of attrition, for outcomes such as bioefficacy, it may not be feasible to test large numbers of nets. If sampling is done at the household level and all nets in the household are sampled, the sample size should be adjusted for design effect and the questionnaire adjusted accordingly.

A sample of 250 LLINs per product will allow detection of a 10% point difference in LLINs attrition rate if the best-performing product has an attrition rate of 10%. This sample size will also allow detection of a 12% point difference in LLINs attrition rate if the best-performing product has an attrition rate of 20%. A list of additional households should be generated from the master list as alternatives for refusals and the absence of a person to interview. The number of nets available for monitoring fabric integrity will decrease over time; however, as observed in previous studies, the fabric integrity of surviving nets is not expected

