### 5.3.1 In case I

Each net will be tested for wash resistance and bio-efficacy once every two months for a total of 12 months (this is case I). The bimonthly washing and bio-efficacy will be conducted in two groups:

- a) Washing to be conducted by trained persons using the standard procedure with close supervision,
- b) Washing to be conducted by the users themselves by instructing them with the method of washing.

Each net will be washed using the protocol described above, according to the schedule outlined in Table 1. Standard WHO cone bioassay will be performed on 30 randomly selected nets of each type at the start of the project and every two months for bioassay, wash resistance and physical inspection. The bioassay will be performed according to the established regeneration time for each net type thereafter cones will be placed in sub sampling locations on each net as shown in Annex 2.

Five susceptible, non-blood fed, two to five day old female susceptible *Anopheles arebiensis* mosquitoes exposed to the net for three minutes, after which they are held for 24 hours with access to the sugar solution. At least 50 mosquitoes on each net (10 replicates) and samples from different type of nets will be tested.

The results will be reported for each net tested along with the pooled results (5 x  $10 \times 4 = 200$  mosquitoes). The number of mosquitoes KD will be counted 60 minutes after exposure, and mortality (functional and effective) after 24 hours of recovery period will be recorded. An average mortality and KD value for each treatment group will then be calculated based on the number of nets for each group (WHO, 2013.1). Bioassay data for each of the sub-sampling locations on the net will also be analysed separately to see if there is a specific trend which may be indicative of more insecticide loss in lower parts of the net due to physical abrasion or lower and central parts of the net due to physical handling. Mosquitoes exposed to untreated nets will be used as controls. If mortality for a given day is between 5% and 20% on the control net it is corrected by an Abbot's formula, if mortality for a given day is > 20% all bioassays carried out on that day will be repeated. The same mosquito strain will be used throughout the study.

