#### 5.5.2 For Case II

Chemical assays (Mandatory) for case II have also done at the beginning of the trial to ensure that the target dose of the insecticide has been achieved, as well as at the completion of the project. For this purpose, four samples (30cm² x 30cm²) are cut along a diagonal across the roof and three samples along a diagonal across each side of 10 randomly selected nets, using sharp scissors. The samples are rolled up and placed in labelled, new, clean aluminium foil prior to assay. The samples from each net will be combined to provide the average target concentration of the insecticide on each net. The number of nets required for chemical analysis is given in table 2 and 3

Measuring the, levels of insecticide will be done using High Pressure Liquid Chromatography (HPLC) or other appropriate testing procedure recommended by the manufacturer of the specific net type at the London School of Hygiene and Tropical Medicine or elsewhere the service is available. An attempt will also be made to do the duplicate locally.

**Table2**. Number of nets required for chemical analysis for case I

	Number of nets required for code I	Number of nets required for code II
Baseline chemical analysis at the start of the study	5nets	5nets
LLINs after a year	10 nets	10 nets

Table3. Number of nets required for chemical analysis for case II

	Number of nets required for code I	Number of nets required for the code
		II
Base line chemical analysis at the start of the study	5 nets	5 nets
LLINs after three years	10 nets	10 nets

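### The 30 bioassay nets and, above all, the 10 end-of-study chemistry nets per product are drawn with no site stratum, so the site mix is left to chance although sites are chosen to represent different settings

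*Protocol*

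**What the plan says.** - **Bioassay.** Protocol 5.3.1 (Case I): "Standard WHO cone bioassay will be performed on 30 randomly selected nets of each type", at the start and every two months. Protocol 5.3.2 (Case II): "The bioassay will be carried on randomly selected 30 sample nets from each type every six months".
- **Chemistry.** Protocol 5.5.2 takes its samples from the roof and sides "of 10 randomly selected nets, using sharp scissors". Tables 2 and 3 give 5 nets at baseline and 10 at the end for each code, read here as each product.
- **Frame.** Protocol 4.3 has the nets for insecticidal testing taken at random from those assessed for fabric integrity, ideally from a roster of the study's nets. For households it says: "Sampling should be simple random sampling, so that there is an equal probability of selection of each household in the list".
- **Settings.** Protocol 4.1: "The sites should represent the environments and cultural settings in which LLINs can be distributed". Of the objectives in 3.2, the one that depends on the chemistry nets reads: "Evaluate the insecticide content at the beginning and over time as they are routinely used by people in various settings".

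No section stratifies either draw by site or village, or sets a minimum per site.

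**The concern.** The protocol takes care to choose sites that differ, then takes small laboratory samples in a way that ignores site. With 10 nets, a whole site may contribute nothing to the insecticide-content result, and that setting then has no end-of-study measurement. With 30 nets, every site will usually contribute, but some by only two or three nets, and in different numbers for different products. Part of an observed difference between products can then reflect which sites happened to supply the nets. Nets withdrawn for testing are lost to follow-up (4.2), so the draw should be settled before withdrawals begin.

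**Working it through.** **Inputs from the protocol.** n = 30 bioassay nets per type per round (5.3.1, 5.3.2). n = 10 end-of-study chemistry nets (5.5.2, Tables 2 and 3). 250 nets per product at the start, and at least 150 left with 40% attrition (4.3): 250 × (1 − 0.40) = 150, which agrees. No derivation is given for the 30 or the 10, so there is no figure to reproduce for them.

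**Assumptions.** The number of sites K is not stated, so a range is shown. Sites are taken as equal in size unless noted.

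**1. Chance that at least one site gets no net.** For a very large frame:

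P = Σ (j = 1 to K) (−1)^(j+1) × C(K, j) × (1 − j/K)^n

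For a frame of N nets drawn without replacement, (1 − j/K)^n becomes C(N − jN/K, n) / C(N, n), with N rounded down to a multiple of K.

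Example, K = 5, n = 10, large frame: 5 × 0.8^10 − 10 × 0.6^10 + 10 × 0.4^10 − 5 × 0.2^10 = 0.5369 − 0.0605 + 0.0010 − 0.0000 = 0.477.

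| Sites | 10 nets: large frame | N = 250 | N = 150 | 30 nets: large frame | N = 250 | N = 150 |
|---|---|---|---|---|---|---|
| 3 | 5.2% | 4.7% | 4.4% | <0.1% | <0.1% | <0.1% |
| 4 | 21.9% | 20.7% | 19.8% | 0.1% | <0.1% | <0.1% |
| 5 | 47.7% | 46.0% | 44.8% | 0.6% | 0.4% | 0.3% |
| 6 | 72.8% | 71.3% | 70.2% | 2.5% | 1.7% | 1.3% |
| 8 | 97.2% | 96.8% | 96.6% | 14.1% | 10.8% | 8.6% |

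With unequal sites, one holding 10% of the nets is missed by 0.9^10 = 35% of chemistry draws and 0.9^30 = 4% of bioassay draws.

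**2. Thin and unequal counts in the bioassay draw (5 sites, 6 nets expected at each; simulation).** Some site has 3 or fewer nets in 54% of draws (large frame), 48% (N = 250) or 44% (N = 150). Two products differ by 4 or more nets at some site in 72%, 67% or 63%.

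**3. Precision of the overall pass share, n = 30.** Under simple random sampling the variance is p(1 − p)/n. Under proportional stratification it is the mean of p_k(1 − p_k) over sites, divided by n. Both sets of site pass shares below are assumed and average 80%, so p(1 − p) = 0.160.
- Shares 95, 90, 80, 70, 65%: mean p_k(1 − p_k) = 0.147. Ratio 0.147/0.160 = 0.919, a gain of 8%. Standard error 7.3 against 7.0 points.
- Shares 100, 95, 80, 65, 60%: mean 0.135. Ratio 0.844, a gain of 16%. Standard error 7.3 against 6.7 points.

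**4. Equal numbers per site when sites are unequal.** Take sites of 60/30/10% and 10 bioassay nets from each.
- If 85% pass everywhere, the weighted estimate has standard error 0.0766 against 0.0652 for simple random sampling: variance ratio (0.0766/0.0652)² = 1.38.
- If pass shares are 90/80/60%, the true share is 0.6 × 90 + 0.3 × 80 + 0.1 × 60 = 84.0%. The unweighted mean is (90 + 80 + 60)/3 = 76.7%, on the other side of 80%.

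**The case against.** The strongest reply is that a simple random draw is sound for the decision the protocol makes. The criterion in 5.3.1 and 5.3.2 is an overall share of nets against 80%, and the draw estimates that share without bias. Chance variation in site mix is already part of its sampling error. This stands: the case for stratifying the bioassay nets is precision and balance, not validity.

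A second reply is that pooling over sites is an inference. Section 4.1 wants a site large enough to supply sufficient nets during follow-up, and 4.3 speaks of differences in a given setting; both could fit a draw made within each site. This is possible, but a total per type together with one roster of the study's nets reads more naturally as a single draw. If a per-site draw is meant, one sentence settles it.

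Third, the objective on insecticide content describes where nets are used and does not promise an estimate for each site. That is fair, but a site with no assayed net adds nothing to that objective. No pass rule is attached to the chemistry, and 5.5.1 gives the Case I assays a supporting role in interpretation, so the consequence is a gap in the evidence, not a wrong pass or fail.

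A reader might also go further than the document allows:
- That whole settings go unmeasured in the bioassay. With 30 nets this is rare up to about 6 equal sites.
- That one product could be judged mostly on one site's nets. With 5 equal sites, the chance that any site supplies more than 15 of the 30 is about 0.02% or less.
- That the survivorship and fabric-integrity objective is affected. It rests on the larger follow-up sample. The bio-efficacy objective names no settings.

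**Conclusion.** The point holds, mainly for the 10 end-of-study chemistry nets. From about 4 equal-sized sites, the chance of leaving at least one site unmeasured is material: 20–22% at 4 sites, 45–48% at 5 and 70–73% at 6, against 4–5% at 3. For the 30 bioassay nets the effect is uneven site counts between products and a variance about 8–16% larger than necessary in the assumed scenarios. It would be wrong to infer that the 80% rule is biased.

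All probabilities depend on a site count that the protocol does not give. They also assume equal sites; a small site is missed more often. This is a cheap improvement to a workable design, worth making before nets are withdrawn. It does not invalidate the trial.

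**What to change.** Add to 5.3.1, 5.3.2 and the end-of-study draw in 5.5: for each product, nets are selected at random within study site, in numbers proportional to site size, with the same plan for every product and at least one net per site where the number of sites allows.

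- **Examples.** With five equal sites: 6 bioassay and 2 chemistry nets per site and product. With sites of 60/30/10%: 18, 9 and 3 bioassay nets, and 6, 3 and 1 chemistry nets.
- **Weighting.** Where the allocation is not proportional, for instance because of the one-net minimum, weight the overall share by site size. Equal numbers per site should not be averaged unweighted when sites differ in size.
- **Reporting.** Give results by site alongside the overall result, as description only where a site has 2 or 3 nets.
- **Limits.** Ten chemistry nets cannot cover more than 10 sites. The baseline chemistry nets check the target dose and need no stratification.

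**Cost.** The number of nets and tests is unchanged. Field organisation and travel rise slightly, because every site contributes at each round.

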## 5.4 Tunnel tests

Tunnel test done for insecticides that have a high excito-repellent effect, such as permethrin and etofenprox. Therefore, the efficacy or mortality and blood feeding inhibition of LLINs that no longer meet the criteria of standard cone bioassays will be studied in the laboratory, by releasing non-blood fed female *Anopheline arebiansis* mosquitoes, aged 5 - 8 days, in a tunnel (square section 25cm x 25cm) made of glass, 60 cm length. At each end of the tunnel, a 25cm square cage is fitted with extension and covered with polyester netting.

At one third of the length, a disposable cardboard frame is placed in the treated netting sample. The surface of netting "available" to mosquitoes is 400 cm^2 (20cm x 20cm), with nine holes each one cm in diameter, one hole is located at the centre of the square; the other eight are equidistant and located at five cm from the border. In the short section of the tunnel, a bait unable to move is placed in the cage at the end of the long section of the tunnel, 100 females are introduced at 18:00. Females *An. arebiansis* will be released to fly in the tunnel, but have to make contact with the piece of netting and locate the holes in it before passing through to reach the bait.

The following morning, at 09:00, the mosquitoes are removed and counted separately from each section of the tunnel and the immediate mortality is recorded. Live females are placed in plastic cups with honey solution; delayed mortality is recorded after 24 hours. During tests, cages are maintained at  $27^{\circ}$ C  $\pm 2^{\circ}$ C and  $80\%\pm 10\%$  RH under subdued light. Several tunnels will be used simultaneously, one tunnel with untreated netting always being used as a negative control. Blood-feeding inhibition is assessed by comparing the proportion of blood-fed females alive or dead in treated and control tunnels. Overall mortality is measured by pooling the immediate and delayed (24hour) mortalities of mosquitoes from the two sections of the tunnel (Annex 2).

# 5.5 Chemical assay 5.5.1 For Case I

Chemical assays of the total insecticide content of the netting following the methodology recommended by the manufacturer and WHO before and after the wash resistance and longevity study will support better interpretation of the results. For this purpose, four samples (30cm x 30cm) will be cut from positions 1up to 4 as outlined in Annex 2, using sharp scissors. The samples will be rolled up and placed in labelled, new, clean aluminium foil prior to analysis. The samples from each net will be combined to provide the average target concentration of the insecticide on the net. Where the target concentration of insecticide is not uniform for the whole net and/or if another chemical is used (i.e., For a combined net), the average target concentration will be calculated separately for the different sections of the net and for each chemical. The number of nets required for chemical analysis is given in table 2 for case I and table 3 for case II.

#### 5.5.2 For Case II

Chemical assays (Mandatory) for case II have also done at the beginning of the trial to ensure that the target dose of the insecticide has been achieved, as well as at the completion of the project. For this purpose, four samples (30cm² x 30cm²) are cut along a diagonal across the roof and three samples along a diagonal across each side of 10 randomly selected nets, using sharp scissors. The samples are rolled up and placed in labelled, new, clean aluminium foil prior to assay. The samples from each net will be combined to provide the average target concentration of the insecticide on each net. The number of nets required for chemical analysis is given in table 2 and 3

Measuring the, levels of insecticide will be done using High Pressure Liquid Chromatography (HPLC) or other appropriate testing procedure recommended by the manufacturer of the specific net type at the London School of Hygiene and Tropical Medicine or elsewhere the service is available. An attempt will also be made to do the duplicate locally.

**Table2**. Number of nets required for chemical analysis for case I

	Number of nets required for code I	Number of nets required for code II
Baseline chemical analysis at the start of the study	5nets	5nets
LLINs after a year	10 nets	10 nets

Table3. Number of nets required for chemical analysis for case II

	Number of nets required for code I	Number of nets required for the code
		II
Base line chemical analysis at the start of the study	5 nets	5 nets
LLINs after three years	10 nets	10 nets

# 6. Adaptations for LLINs with novel insecticides, synergists and insecticide mixtures

LLINs with new active ingredients or mixed formulations may have different mechanisms of action and performance criteria. Some novel LLINs are well understood and familiar, and these can be assessed with established WHOPES methods and criteria. LLINs that have new intended functions or purposes (e.g. formulations with a synergist), however, will require additional test procedures and criteria. The mechanism of action is entirely different and the conditions for effectiveness are not yet known (e.g. LLINs with slow-acting insecticides), epidemiological evidence of effect on malaria or other vector borne diseases (proof of principle) may be required. The present document provides guidance for evaluating anticipated LLINs products with new insecticides or combinations of insecticides that may become part of a resistance management strategy.

### 6.1 Characterization of insecticide resistance

New, non-pyrethroid insecticides brought to the public health pesticides market must be tested against a range of resistant mosquito strains in this studies. Therefore, new mosquito strains with novel resistance mechanisms should be established and characterized. Ideally, resistant strains should be characterized by target site modification (e.g. kdr) and the presence of different metabolic resistance mechanisms. Phenotypic resistance should be measured just before the trial or within the 6 months before the trial. In this studies, phenotypic resistance should be measured before distribution of nets, at the mid-point of the study and at the end of the study.

# 6.2 Efficacy testing of nets with insecticides other than pyrethroids

LLINs may contain compounds with entirely new modes of action on mosquitoes. If the new insecticide acts primarily through contact toxicity, like pyrethroids, causing rapid knock-down and mortality, the general framework for evaluating LLINs will be applicable, although modifications may be required in each steps of testing. LLINs products that act by causing mortality alone, repellence alone or by an alternative mode of action on mosquitoes, may require, as proof of principle, epidemiological studies to demonstrate their efficacy in reducing malaria transmission or in controlling the disease. A number of modifications are recommended to this studies for LLINs containing novel insecticides. This type of testing is designed to assess the efficacy, wash resistance and regeneration time of the insecticide on the netting. The current guidelines recommend that LLINs be tested against susceptible strains of mosquitoes. When new insecticides are used in the manufacture of LLINs, cross-resistance to other insecticides should be assessed. It may be necessary to modify certain test procedures, depending on the mode of action of the new insecticide. For example, for LLINs with slow-acting insecticides, mortality may be recorded 24, 48 and 72 h after exposure. For LLINs that contain growth regulators, it may be necessary to measure the fertility and fecundity of females exposed to the netting. In this studies, the efficacy of LLINs should be determined against wild, free-flying mosquitoes susceptible both to pyrerthroids (where possible, given the spread of pyrethroid resistance) and to the insecticide on the candidate LLINs. The recommendations for the studies of pyrethroid-treated LLINs should be followed, although some modifications may be required, depending on the mode of action of the insecticide on the novel LLINs. The reference LLINs should be a WHOPES-recommended net with the same or similar specifications in terms of netting material, denier and mesh size. Currently, the reference LLINs will necessarily be a pyrethroid-treated LLINs. As LLINs containing novel insecticides with new modes of action become available, further modification of these guidelines and evaluation methods may be necessary.

A net will be considered to have met the requirements for WHO interim recommendation if the mortality and blood-feeding inhibition of the candidate LLINs washed 20 times is equal to or better than that of the positive control washed 20 times.23 If the candidate LLINs meets these criteria when tested against a vector population that is susceptible to both pyrethroids and the novel compound, further tests should be conducted in areas where the vector population is resistant to pyrethroids but susceptible to the novel compound. Where pyrethroid-susceptible populations are not available for testing, a reference LLINs should still be included in the comparison as best

practice; however, the decision to recommend the novel product as an LLINs will be made on the basis of its own performance. This studies should include a positive control LLINs arm as recommended above, and WHO cone bioassays and tunnel tests should be done with pyrethroid-susceptible and pyrethroid-resistant strains. The susceptible strain serves for quality control, while the resistant strain is used to estimate the durability of the candidate LLINs under field conditions. Laboratory evaluations of novel LLINs may have to be modified. As noted above, candidate LLINs treated with insecticides with effects on mosquitoes that differ from those of pyrethroids may require proof of principle and new assays.

